6.1 Surgical Visit

After the study drug is administered (~1-3 hours prior to surgery), the patient will be prepared and transported to surgery as per routine at Dartmouth-Hitchcock. In the OR, patient positioning, registration of the MR image-guidance system, preparation of the surgical field, and draping will follow standard practice, as will scalp incision and craniotomy. Upon opening of the dura, the coregistered and tracked Zeiss Pentero operating microscope adapted for intraoperative fluorescence imaging (iFI) at 800 nm will be brought in to begin conventional image-guided microsurgical technique for tumor resection. At approximately 4 time points during each surgery and/or at the discretion of the surgeon, data/image and specimen acquisitions will occur. Three (3) will typically occur at first exposure of tumor, at the approximate mid-point of tumor resection (when a significant tumor tissue is in the field), and at a point nearing but prior to completion of tumor resection (when small amount of tumor tissue remains), and a fourth may occur at presumed end of resection. At each time point, iFI acquisitions will be recorded. The surgeon will then focus the coregistered microscope at discrete points in the operative field which exhibit non-, weakly, moderately, and strongly fluorescent emissions, if evident on the iFI scan. At each point, a second iFI will be acquired, optical probe measurements will be recorded and a surgical biopsy specimen will be obtained (except at presumed end of resection when no more tissue is planned for excision). Since the 2nd iFI, probe data and biopsy sample will occur each time at the focal point of surgical microscope which is coregistered, all intraoperative images, data and specimens will also be coregistered. If no signal is evident on the iFI scan, the surgeon will sample several locations in the surgical field by focusing the operating microscope on points of interest intended for resection, performing the probe measurements and biopsying the positions for later analysis. iFI and optical probe readings will also be acquired from normal brain to establish baseline/background signal levels for the case. Additionally, an imaging module mounted on a second commercial, clinical microscope, will be used to acquire images during surgery. Acquiring these images will involve moving the primary clinical scope out of the field, positioning the new scope to acquire images, and moving the primary scope back into place. This process will take approximately three minutes or less and poses no additional risk to the patient. When the case is performed in the Center for Surgical Innovation, and when indicated clinically, iMR (intraoperative MRI) may be acquired and resection may continue based on the findings. In these cases, iFI, optical probe and biopsy may occur at locations planned for resection. We have used these same coregistered image, data, and biopsy procedures in our current studies of ALA-induced PpIX fluorescence and have collected high quality information from up to 12-16 surgical specimens per case (~10 on average).

6.1.1 Specimen Preparation and Handling

Resected specimens used for standard clinical care will be analyzed according to practice. Tissues taken as part of the study will be bisected immediately in the OR into nearly equivalent pieces in terms of size and gross appearance with one part going into 10% buffered formalin and the other snap frozen in liquid nitrogen. If the specimen cannot be divided, the sample will be formalin-fixed.

6.2 Clinical Laboratory and Monitoring Data

Since the microdoses that will be administered are presumed to fall below levels needed to cause pharmacological and/or physiological responses/effects that increase subject risks, and the preclinical (rodent) results from the Dartmouth Toxicity Study showed no evidence of systemic toxicity, either histologically or in terms of blood chemistry (in the latter, some clinical chemistry values in dosed animals were statistically different from un-dosed controls at 24 hours, but all levels were well within the normal range) associated with much higher single-doses of ABY-029 (10X, 100X, 1000X), no protocol-specific clinical laboratory or monitoring data associated, for example, with renal or liver function will be collected. Data obtained in this patient group as part of standard-of-care laboratory studies and clinical monitoring procedures includes hemoglobin, hematocrit, white blood cell count, platelet count, electrolytes (sodium, potassium, chloride, bicarbonate), glucose, BUN and creatinine prior to administration of ABY-029. Similarly, vital signs (heart rate, blood pressure, respiratory rate) are monitored pre-operatively, during

surgery and post-operatively in the Neurosurgical Special Care Unit for a minimum of 24 hours following surgery as part of standard-of-care, and these data are available for adverse event monitoring. EKGs, when collected as part of standard-of-care operating procedures on surgical patients at Dartmouth-Hitchcock, are available pre-operatively, monitored continuously during surgery and again post-operatively (typically in the evening of the day of surgery). These data will not be collected as part of this clinical protocol per se, but will be available for adverse event monitoring, as needed.

6.3 Specimen Analysis

Biopsy samples taken at the time of surgery for research purposes and processed for IHC will be scored by a pathologist according to the following criteria: 0 = no staining; 1 = low membranous staining around cells; 2 = medium membranous staining completely around cells; and 3 = high membranous staining completely around cells. Standard formalin-fixation with paraffin embedding will be used for histopathologic type and grade to confirm diagnosis of astrocytoma or glioblastoma (following WHO criteria) by the study neuropathologist. As these tumors are recurrences and patients have received radiation and chemotherapy, an assessment of reactive gliosis vs. residual/recurrent glioma will also be scored as well as tumor burden and necrosis using methods previously described. Here, histopathology will be classified as non-tumor tissue, solid tumor, infiltrating tumor, or indeterminate. Infiltrating tumor will be further graded into <33% tumor, >33% but <67% tumor, and >67% tumor). Proliferation will be assessed by quantitatively scoring Ki-67 immunopositive cells. ABY-029 binding to tumor cells in the specimen will be evaluated by performing IHC with secondary antibodies directed against the anti-EGFR Affibody following the protocol. EGFR protein expression often corresponds to gene amplification, thus, we will assess gene-protein correlations on a cell-by-cell basis by performing both IHC for EGFR protein and CISH for EGFR gene amplifications using a multi-spectral analysis microscope (Nuance) to distinguish in individual tumor cells. Frozen tissue will be solubilized and evaluated for quantitative fluorescence using fluorimetry. Western and/or ELISA will be used if the signal is not sufficiently strong.

7 Statistical Plan

7.1 Sample Size Determination

Sample size determination is based on the primary objective of the study as a pilot assessment of fluorescence detection of ABY-029 localization in EGFR+ tumors with iFI. We estimate a minimum of 6, and more typically 12-16 specimens per case will be collected, and assume an average of 10 is available consistent with numbers in similar studies of ALA-induced PpIX fluorescence that have enrolled over 100 subjects. To assess the adequacy of this sample size, if only 3 patients are enrolled at a specific dose, the study will have 80% power to detect a difference in fluorescence signal mean in samples relative to normal brain as small as 3.3 standard deviations with a two-sided significance level of 0.05, and a difference in fluorescence signal mean in samples between two EGFR pathology scoring levels of 2.7 standard deviation with the same power and significance level (assuming samples are equally distributed between EGFR pathology scoring levels). If 6 patients are enrolled a one dose, the detectable difference in fluorescence signal mean in samples relative to normal brain drops to 1.4 standard deviations (at the same power and significance level) and to 1.8 standard deviations for differences in signal mean between two EGFR pathology scoring levels.

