7.2 Data and Statistical Analysis

The primary study objective is to relate ABY-029 fluorescence (resulting from a specific pre-surgical dose) measured by wide-field iFI to EGFR pathology score (based on IHC staining) of coregistered tissue specimens sampled at the same time points during surgery. Similar but more sensitive fluorescence data will be available from the intraoperative optical probe. A minimum of 3 patients will be enrolled at a given dose, and up to 6 patients may be enrolled at one dose, if iFI SNR requirements are met. Assuming 10 specimens are available for analysis on average from the surgical cases at a given dose (this value is consistent with average specimen counts in related ALA-induced PpIX studies which have enrolled more than 100 subjects), 30 specimens with corresponding probe signals and IHC pathological scoring will be available for analysis, and as many as 60 specimens may exist, if iFI SNR goals are achieved. Clustered

data analyses of variance will be performed to account for multiple samples from each patient. Student's t-test evaluation will be used to determine signal detectability relative to measurements in normal brain, and relative to the noise floor of the iFI system determined from laboratory measurements in phantoms. ANOVA will also be used to assess differences in signal means when stratified by EGFR pathology score (0 = no expression, 1 = low expression, 2 = medium expression, 3 = high expression). Pearson's and Spearman's rank correlations between iFI signal strength and EGFR pathology score will be computed. These analyses will be repeated for the optical probe data as well.

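### Section 7.1: the 3-patient EGFR-level detectable difference (2.7 SD) does not fit the patient-level t-tests that reproduce the other three figures; on that basis it would be 3.07 SD

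*Combined protocol and SAP*

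**What the plan says.** Section 7.1 (Sample Size Determination) assesses the sample size through four detectable differences in mean fluorescence signal, all at 80% power.

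- **Against normal brain:** with 3 patients at a dose, a difference "relative to normal brain as small as 3.3 standard deviations with a two-sided significance level of 0.05"; with 6, the figure "relative to normal brain drops to 1.4 standard deviations".
- **Between EGFR levels:** with 3 patients, a difference "between two EGFR pathology scoring levels of 2.7 standard deviation with the same power and significance level"; with 6, it falls "to 1.8 standard deviations for differences in signal mean between two EGFR pathology scoring levels".

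The EGFR-level figures carry one condition, "assuming samples are equally distributed between EGFR pathology scoring levels". Section 7.1 also assumes an average of 10 specimens per patient. It does not say which test the figures come from, whether the unit is the patient or the specimen, which standard deviation is meant, or what ICC was used.

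Section 7.2 (Data and Statistical Analysis) plans a Student's t-test against normal brain and analyses of variance that allow for clustering within patient. For the four-category EGFR score it says that "ANOVA will also be used to assess differences in signal means when stratified by EGFR pathology score". Section 6.1 (Surgical Visit) has each patient sampled at "discrete points in the operative field which exhibit non-, weakly, moderately, and strongly fluorescent emissions", so one patient can supply specimens at several EGFR levels.

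**The concern.** Both figures in a pair should come from the same calculation with only the number of patients changed. Because no method is named, the check is to find the calculation that returns the stated values. Ordinary patient-level t-tests return three of the four. The exception is the EGFR-level figure for 3 patients, and it departs in the favourable direction.

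This matters because section 7.1 offers these figures to show that the sample is adequate when only 3 patients are enrolled at a dose. If 2.7 is a slip, the 3-patient case looks stronger than it is. If the pairs rest on different bases, a standard deviation in one pair is not the same quantity as in the other, and the four figures cannot be compared.

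**Working it through.** **Inputs from section 7.1.** Two-sided alpha 0.05; power 80%; 3 or 6 patients at a dose; 10 specimens per patient; equal distribution over EGFR levels. From section 7.2: four score levels (0 to 3). The methods below are inferred, because the documents name none for these figures. All results use the exact noncentral t distribution.

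**Step 1: normal brain, one-sample or paired t-test on patients.** The noncentrality is d × √n with n − 1 df.
- n = 3, df 2: 80% power at d = 3.26 (stated 3.3).
- n = 6, df 5: 80% power at d = 1.43 (stated 1.4).

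Both figures are reproduced.

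**Step 2: EGFR levels, two-sample t-test, one value per patient and level.** The noncentrality is d × √(n/2) with 2n − 2 df.
- n = 6 per level, df 10: d = 1.80 (stated 1.8). Reproduced; power at 1.8 is 80.2%.
- n = 3 per level, df 4: d = 3.07 (stated 2.7). Not reproduced.

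The gap is 3.07 − 2.70 = 0.37 SD, and 0.37 / 2.70 = 14%. At d = 2.7 the noncentrality is 2.7 × √1.5 = 3.31, and power is 69.9%. If the unrounded figure lay anywhere from 2.65 to 2.75, power is 68.4% to 71.4%. At 3.1 SD it is 80.7%.

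**Step 3: other patient-level forms.** After rounding, the ratio of the stated pair lies between 2.65/1.85 = 1.43 and 2.75/1.75 = 1.57.

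| Form | 3 patients | 6 patients | Fits 2.7 and 1.8? |
|---|---|---|---|
| ANOVA contrast, error df pooled over 3 independent levels (df 6, 15) | 2.75 | 1.73 | 2.749 rounds to 2.7, but 1.73 rounds to 1.7 |
| Same, 4 independent levels (df 8, 20) | 2.61 | 1.70 | No |
| Paired on patient, two levels | ratio 2.28 at any correlation | | No |
| Blocked by patient, three levels | ratio 1.71 at any correlation | | No |
| Blocked by patient, four levels | ratio 1.59 at any correlation | | No |

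In the paired and blocked forms the contrast variance is 2(1 − ρ)/n. The within-patient correlation ρ therefore scales both figures equally and leaves the ratio unchanged.

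**Step 4: specimen-level t-test with a design effect.** Take 10 specimens per patient over four equal levels, so 2.5 per patient per level. Use a design effect of 1 + (5 − 1) × ICC, counting the 5 specimens per patient in the two levels compared, with an assumed ICC of 0.5.
- Design effect: 1 + 4 × 0.5 = 3.
- 3 patients: 7.5 specimens per level, effective 7.5/3 = 2.5, df 2 × 7.5 − 2 = 13, giving d = 2.71.
- 6 patients: 15 per level, effective 15/3 = 5, df 28, giving d = 1.84.

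These round to 2.7 and 1.8. With this set-up, both figures are matched for an ICC of 0.47 to 0.51. Other set-ups with 10 specimens match at 0.21 to 0.225 (2.5 per level, design effect for 10) and at 0.585 to 0.59 (5 per level, design effect for 10).

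Each match needs two conventions: df counted from specimens as if independent, and a design-effect cluster size larger than the number of specimens per patient in one level. With cluster size equal to the per-level count (2.5 with 2.5, or 5 with 5), or with df from patients or from the effective sample size, no ICC matches both.

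**Step 5: can that method also give the normal-brain pair?** No. The one-sample specimen-level form with specimen df has a 3-to-6-patient ratio of 1.44 to 1.56. The stated pair needs 3.25/1.45 = 2.24 to 3.35/1.35 = 2.48. Even an ICC of 1 gives only 1.67 and 1.16 SD.

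**The case against.** The strongest reply is that a clustered, specimen-level calculation is close to what the plan describes. Section 7.1 speaks of signal in samples, assumes 10 specimens per patient and spreads them equally over levels; section 7.2 plans clustered analyses over four scores. At the round value ICC = 0.5 that calculation rounds to both 2.7 and 1.8. Two figures given to one decimal will fit any continuous parameter only in a narrow window, so narrowness alone is weak evidence against it. Section 7.2 also names different analyses for the two comparisons, so a different basis for each pair would not be strange.

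Much of this stands. A reader might infer that no single method can give both EGFR-level figures; step 4 shows that one can. A reader might also infer that 2.7 is proven wrong; the documents do not show that, because the two-sample basis is inferred. That basis treats the two levels as independent sets of patients, although the same 3 or 6 patients would supply both. Nor is 70% the power of the study whatever the method. At 2.7 SD it is 78.6% or 82.5% with error df pooled over three or four independent levels, and 44%, 67% or 84% for a paired test at assumed within-patient correlations of 0, 0.5 or 0.7.

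What the reply does not do is make section 7.1 consistent as written. It needs an ICC that the plan never states, the two conventions in step 4, and a second unstated basis for 3.3 and 1.4. It shows that a single method for the EGFR pair is possible, not that it was used.

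**Conclusion.** The 3-patient EGFR-level figure is inconsistent with the simple patient-level t-tests that reproduce the other three. On the two-sample test that gives 1.8 SD for 6 patients, the matching 3-patient figure is 3.07 SD, and 2.7 SD carries about 70% power instead of 80%. The only textbook calculation found that rounds to both EGFR figures is the specimen-level design effect at a particular unstated ICC, and it cannot give the normal-brain pair. Either 2.7 is a slip or the section mixes unstated bases, and the documents do not settle which.

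Severity is minor and confidence moderate. The arithmetic is firm; the basis is inferred. A reader might take this to undermine the design, but the documents do not support that: section 7.1 is an adequacy statement for a pilot, and dose steps and enrolment follow the signal-to-noise rule in section 1.5, which uses none of these figures.

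**What to change.** The sponsor's statistician should confirm how the four figures were obtained.

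- If the EGFR-level pair came from the two-sample patient-level test, restate 2.7 SD as 3.1 SD and name the tests.
- Otherwise, recompute all four figures on a stated basis: the unit of analysis, which standard deviation is meant, the ICC, and how the calculation allows for the same patients supplying several EGFR levels. For example, patient-level ANOVA pooled over three independent levels would give 2.7 and 1.7 for the EGFR pair.

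The cost is one corrected number, or one sentence and a recomputed set of four, in section 7.1. It adds no patients and changes no dose step or analysis. The only downside is that, on the two-sample basis, the stated 3-patient figure becomes slightly less favourable.

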7.2 Data and Statistical Analysis

The primary study objective is to relate ABY-029 fluorescence (resulting from a specific pre-surgical dose) measured by wide-field iFI to EGFR pathology score (based on IHC staining) of coregistered tissue specimens sampled at the same time points during surgery. Similar but more sensitive fluorescence data will be available from the intraoperative optical probe. A minimum of 3 patients will be enrolled at a given dose, and up to 6 patients may be enrolled at one dose, if iFI SNR requirements are met. Assuming 10 specimens are available for analysis on average from the surgical cases at a given dose (this value is consistent with average specimen counts in related ALA-induced PpIX studies which have enrolled more than 100 subjects), 30 specimens with corresponding probe signals and IHC pathological scoring will be available for analysis, and as many as 60 specimens may exist, if iFI SNR goals are achieved. Clustered

data analyses of variance will be performed to account for multiple samples from each patient. Student's t-test evaluation will be used to determine signal detectability relative to measurements in normal brain, and relative to the noise floor of the iFI system determined from laboratory measurements in phantoms. ANOVA will also be used to assess differences in signal means when stratified by EGFR pathology score (0 = no expression, 1 = low expression, 2 = medium expression, 3 = high expression). Pearson's and Spearman's rank correlations between iFI signal strength and EGFR pathology score will be computed. These analyses will be repeated for the optical probe data as well.

Secondary study objectives will be assessed by performing analyses on the iFI and probe data as a diagnostic test with the corresponding specimen histopathological diagnoses as the gold standard. Predictive models (for each pathology) of the odds of tumor positivity for biopsies given concentration of ABY-029 will be constructed. Histologically confirmed tumor status from biopsies will be treated as a binary outcome with a logit link function in a generalized linear mixed model (SAS GLIMMIX) with a subject-specific random effect to account for intra-individual correlations among biopsies. The iFI and/or probe fluorescence measures will be introduced first as linear terms. Interactions and polynomial fits will also be assessed via goodness of fit statistics. The predictive accuracy of the model fit will be summarized through a concordance index, i.e., area under the ROC curve formed with the fitted probabilities of tumor. Analyses will be repeated for other histopathological indicators (beyond tumor/non-tumor) such as degree of proliferation, infiltration, ABY-029 binding, among others.

7.3 *Subject Population(s) for Analysis*

This study will involve patients with recurrent intra-cranial malignant glioma judged to be operable. Subjects eligible for enrollment in the trial will be patients with a previously resected high grade glioma with tissue positive for EGFR expression (pathology score ≥ 1 based on histological staining).

8 Safety and Adverse Events

The study will be monitored by the Data, Safety Monitoring, and Accrual Committee (DSMAC) of the Norris Cotton Cancer Center at Dartmouth-Hitchcock Medical Center. All unexpected and/or serious adverse events will be reported to committee by the protocol PI or the designee, along with a determination of their relationship to study procedures. Given that brain tumor patients undergoing open surgical resection procedures present with post-operative complications and medical events that are expected, we will log and review all adverse events, but evaluate and report on only those with outcomes that would not routinely be expected in this surgical patient population to the NCCC DSMAC, along with a determination of their probable relationship to study procedures. Summaries of study enrollments, clinical status, and data will be submitted for annual review (or more frequently as required depending on enrollment patterns). In the case of any unexpected adverse events, the patient's medical record will be reviewed by a study physician, and if necessary, the patient will be examined by a study physician and appropriate medical action taken. The event will be recorded in the patient's study file with the date of occurrence, date of resolution, severity and the actions taken. Any unexpected or serious adverse events, or drug reaction beyond those expected from open-cranial brain tumor surgery that are determined likely to be related to the study procedures, will be reported to the Dartmouth IRB and the FDA as required.

9 Data Handling and Record Keeping

9.1 *Confidentiality*

Information about study subjects will be kept confidential and managed according to the requirements of the Health Insurance Portability and Accountability Act of 1996 (HIPAA). Risk of breach of confidentiality of the medical records and status of participants will be minimized. Databases which are used to store subject-sensitive information are password-protected and encrypted during file/data transfers from viewing terminals. Access will be limited to research team members who have undergone CPHS training at Dartmouth. Whenever possible and practical standard-of-care clinical data used in the research will be de-identified when under analysis.

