Short Title	A Microdose Evaluation Study of ABY-029 in Recurrent Glioma
Protocol Number	N/A
Phase	Phase 0 microdose
Methodology	Patients will be administered a single intravenous dose of ABY-029 1-3 hours before surgery. At different times during resection, the coregistered surgical microscope (Zeiss Pentero enabled with intraoperative fluorescence imaging, iFI) will be focused on a point of interest. The surgeon will switch to iFI mode to capture images of the surgical field. Quantitative measurements of fluorophore concentration will be made at the focal point of the operating microscope with an intraoperative probe and biopsy samples will be taken at the coregistered point of interest for subsequent histological analyses and ex-vivo assessments of fluorophore concentration. In addition, an imaging array mounted on second commercial, clinical microscope, will be briefly exchanged with the primary scope to take additional images of the surgical field.
Study Duration	12-18 months
Study Center(s)	Single-center, Dartmouth-Hitchcock Medical Center
Objectives	The primary study objective is to determine if microdoses of ABY-029 (up to 6X) lead to detectable signals (defined as signal-to-noise ratio, SNR ≥ 10 , with wide-field iFI) in sampled tissues with an EGFR pathology score ≥ 1 based on histological staining. The secondary study objective is to assess diagnostic accuracy of ABY-029 detection by iFI and intraoperative probe relative to histopathology diagnosis, and other indicators (e.g. proliferation, infiltration, etc.) as the gold standard, and to measure the molecular uptake and concentration of ABY-029 in resected specimens.
Number of Subjects	A minimum of 6 and a maximum of 12 adult patients with a diagnosis of recurrent glioma will be enrolled.
Diagnosis and Main Inclusion Criteria	Operable brain tumor in adults with pre-surgical diagnosis of recurrent glioma.

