Study Product, Dose, Route, Regimen	
Criteria for successful iFI are locations of all EGFR positive samples (defined as having a pathology score ≥ 1 based on histological staining) having a measurable signal (defined as SNR ≥ 10). A single microdose of ABY-029 at 30 nanomoles (237μg) will be injected into the first 3 patients. If samples from these subjects meet successful iFI criteria, 3 more patients will be enrolled at the same dose, concluding the study with a total of 6 subjects. Otherwise, the ABY-029 dose in the next 3 patients will be increased to 3X (90 nanomoles, 711 μg). If samples from these subjects meet successful iFI criteria, 3 more patients will be enrolled at the 3X dose, concluding the study with a total of 9 subjects. If iFI criteria are not met, the next 3 patients will be enrolled at 6X dose (180 nanomoles, 1.42 mg). If iFI criteria are met, 3 more patients will be enrolled the 6X dose, concluding the study with a total of 12 subjects. If iFI criteria are not met in the first 3 patients at the 6X dose, enrollment will be stopped with a total of 9 subjects.
 
Because of the microdosing levels used, the results of the Dartmouth Toxicity Study (at 10X, 100X, 1000X doses), and the safety profile of similar compounds (e.g. ABY-025), we do not anticipate any serious adverse events (SAEs) related to ABY-029.

Duration of administration	ABY-029 will be administered by IV injection on day of surgery, approximately 1-3 hours prior to the procedure.
Reference methods	Post-operative histopathology will serve as the gold standard.
Statistical Considerations	Repeated measures analyses of variance will be performed to account for multiple samples from each patient. Student's t-test will be used to evaluate ABY-029 fluorescence signal detection in tumor relative to normal brain with iFI and intraoperative probe. Empirical ROC curves and logistic regression analysis for clustered binary data will be used to evaluate the accuracy of ABY-029-specific fluorescence in discriminating between EGFR+ glioma tumor, EGFR- glioma tissue, and normal tissue when detected by iFI and/or intraoperative probe.

1 Introduction

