1.6.2 Potential Benefits

Patients enrolling in this study will not benefit directly because no diagnostic or therapeutic decisions will occur based on the study drug, and thus, administration of the study drug is not intended to alter the extent of planned brain tumor resection during the surgical procedure. However, future patients may benefit from the knowledge gained from the study. Current literature shows that maximum cytoreductive surgery is of significant benefit to patients with malignant gliomas. Patients with complete resections also experience survival benefits from post-operative radiation and/or chemotherapy. Unfortunately, achieving a high degree of tumor removal is often limited by the surgeon's ability to distinguish residual disease from intervening parenchyma under conventional white light illumination, and rates of complete resection have

been reported to be as low as 20% in high grade glioma. iFI augments the surgeon's white light visual field with fluorescent information, and in the case of ALA-induced PpIX, improved patient outcomes in a prospective randomized Phase III trial sufficiently to alter standard-of-care in Germany for surgical resection of high grade glioma. While ALA appears to be effective, motivation exists for pursuing new fluorescent probes beyond PpIX for guiding surgical resection. First, ALA-induced PpIX fluorescence is not tumor-specific. Second, fluorescent enhancement at the margin and in low-grade glioma is relatively poor. Third, ABY-029 has potential to guide a range of oncologic surgeries, given the large number of tumor types that overexpress EGFR. Fourth, a wealth of information exists on EGFR fluorophore targeting which suggests our approach is likely to be successful and could benefit patients with malignant glioma and other cancers whose prognosis is improved by complete surgical resection.

2 Study Objectives

The primary study objective is to determine if microdoses of ABY-029 (up to 6X) lead to detectable signals (defined as signal-to-noise ratio, SNR ≥ 10 , with wide-field iFI) in sampled tissues with an EGFR pathology score ≥ 1 based on histological staining.

The secondary study objectives are to assess the diagnostic accuracy of ABY-029 detection by iFI and an intraoperative probe relative to histopathology as the gold standard, and to measure the molecular uptake and concentration of ABY-029 in resected specimens.

3 Study Design

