3.2 Primary Study Endpoints

The primary study endpoint is signal detection (defined as SNR with wide-field iFI) in vivo in brain tissues within the surgical field intended for resection that are subsequently sampled during surgery and assigned an EGFR pathology score based on histological staining.

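### Section 7.2 restates the primary objective as relating fluorescence to EGFR score, and none of its analyses uses the SNR ≥ 10 cut-off that defines the objective in the synopsis and Section 2

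*Combined protocol and SAP*

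**What the plan says.** - **Section 2 (and the synopsis).** "The primary study objective is to determine if microdoses of ABY-029 (up to 6X) lead to detectable signals", where detectable means iFI SNR ≥ 10, "in sampled tissues with an EGFR pathology score" of at least 1. This is a threshold question about EGFR-positive tissue.
- **Section 3.2.** "The primary study endpoint is signal detection (defined as SNR with wide-field iFI) in vivo in brain tissues". SNR is named, but with no cut-off and no minimum EGFR score.
- **Section 7.1.** The sample size rests on a "pilot assessment of fluorescence detection of ABY-029 localization in EGFR+ tumors with iFI". The wording fits Section 2, but the power figures are for differences in mean signal.
- **Section 7.2.** "The primary study objective is to relate ABY-029 fluorescence (resulting from a specific pre-surgical dose) measured by wide-field iFI to EGFR pathology score". The analyses listed are clustered ANOVA, t-tests, ANOVA by score 0 to 3, and Pearson and Spearman correlations, all repeated for the probe. On detection: "t-test evaluation will be used to determine signal detectability relative to measurements in normal brain", and also relative to the iFI noise floor measured in phantoms. SNR appears only where patient and specimen numbers are discussed, for example "up to 6 patients may be enrolled at one dose, if iFI SNR requirements are met".
- **Dose rule.** The synopsis states: "Criteria for successful iFI are locations of all EGFR positive samples" having SNR ≥ 10. Section 1.5 gives the same scheme, but its definition of success omits the word for all. In both places the rule is checked in the first 3 patients at a dose.

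**The concern.** The plan holds two primary objectives. One asks whether signal in EGFR-positive tissue reaches a stated level. The other asks whether signal varies with EGFR score. A trial can succeed on either and fail on the other: signal may rise with score while every location stays below SNR 10, or every positive location may exceed 10 with no gradient across scores 1 to 3.

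Section 1.5 describes SNR of 10 as a precondition for later work on diagnostic performance, so it is the result a reader will look for. Someone following Section 7.2 as written could report significant t-tests and correlations under the name of the primary objective without saying how often positive tissue reached SNR 10. At an expanded dose, patients 4-6 are the only ones not selected by having passed the rule, and no SNR ≥ 10 result is planned for them.

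**Working it through.** **1. Each Section 7.2 analysis against the Section 2 criterion**

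| Analysis | Uses SNR ≥ 10? | Handling of EGFR score |
|---|---|---|
| t-test against normal brain | No, compares means | No restriction stated |
| t-test against phantom noise floor | No, compares means | No restriction stated |
| ANOVA by score | No, compares means | Separates 0, 1, 2, 3 |
| Pearson, Spearman | No, association | Uses score as a variable |
| Logistic mixed model, ROC area (secondary) | No, outcome is tumor status | Not used |

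No row classifies a location, patient or dose by the cut-off.

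**2. The plan's own power figures**

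A one-sample (paired) t-test on patients, two-sided 0.05, 80% power, noncentral t, gives:
- 3 patients: 3.26 SD (Section 7.1 states 3.3)
- 6 patients: 1.43 SD (Section 7.1 states 1.4)

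So the Section 7.1 figures for samples against normal brain correspond to a patient-level test of a mean difference. They are in units of the spread of the signal and do not fix an SNR. For illustration, if that SD were 1.5 to 3 SNR units (an assumption), 3.3 SD would be 3.3 × 1.5 = 4.95 to 3.3 × 3 = 9.9 SNR units above the comparator, and 1.4 SD would be 2.1 to 4.2.

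**3. Does a significant t-test imply SNR ≥ 10?**

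All SNR inputs here are assumptions: log-normal SNR with median 5, log-SD 0.3 between patients and 0.3 within, 3 patients, 10 positive locations each.

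True share of locations at SNR ≥ 10:
- total log-SD = √(0.3² + 0.3²) = 0.424
- ln(10/5) / 0.424 = 0.693 / 0.424 = 1.63
- share = 1 − Φ(1.63) = 0.051, about 5%

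The t-test is run on the 3 patient means: t = (mean − floor) / (SD/√3), two-sided 0.05, 2 degrees of freedom, critical value 4.30. By simulation:

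| Background level (SNR units) | Share of trials significant |
|---|---|
| 0 | 82% |
| 1 | 67% |
| 2 | 47% |
| 3 | 26% |

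The rate depends heavily on the background level and on the assumed spread. With a zero floor it is about 98% at log-SDs of 0.2 and 47% at 0.5. The conclusion needs only that it can be well above zero when few locations reach SNR 10.

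**4. What a patient-level result would look like**

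Count the patients in whom every EGFR ≥ 1 location reaches SNR ≥ 10. Exact two-sided 95% limits:
- 3 of 3: lower limit 0.025^(1/3) = 0.292, or 29%
- 2 of 3: the lower limit solves 3p² − 2p³ = 0.025, so p = 0.094; the upper limit solves 1 − p³ = 0.025, so p = 0.992; the interval is 9% to 99%
- 6 of 6: lower limit 0.025^(1/6) = 0.541, nominal only, because the first three were selected by passing

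**The case against.** The strongest reply is that this is a combined protocol and SAP, and the criterion is prespecified elsewhere. The synopsis and Section 1.5 define success and state what follows from each outcome, up to stopping enrollment. That stands. A reader might infer from Section 7.2 that the SNR criterion goes unused; the documents do not support this, because it drives every dose decision. What is missing is narrower: an estimate, its uncertainty, and a result for patients 4-6.

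A reader might also infer that Section 7.2 ignores EGFR status. It does not: the ANOVA separates score 0 from scores 1, 2 and 3, and only the t-tests lack a stated restriction.

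A third tempting inference is that the t-test would usually be significant whatever the true SNR. A constant rate arises only if the comparator is exactly zero and the log-SD is fixed, since the test is then unaffected by scale. Section 7.2 compares with measured normal brain and a phantom noise floor, not with zero, so the table above is an illustration and not a forecast for this trial.

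It is also fair to say that a Phase 0 pilot of this size yields wide intervals, and that much of the gap would close with aligned wording and a table. That limits what the interval can show, but it does not remove the need to report the quantity named in the objective.

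**Conclusion.** The point holds and should be fixed. That the primary objective is worded in two ways, and that no Section 7.2 analysis uses SNR ≥ 10, follows from the text and rests on no assumption. The consequence is that the plan's only planned answer on its primary criterion is a yes/no check in the first 3 patients at a dose. Even a pass in 3 of 3 patients is compatible with a true patient-level rate as low as 29% (exact, two-sided 95%).

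The 26% to 82% range shows only that a significant t-test and SNR ≥ 10 are different findings. It rests on an assumed median, spread and number of locations, because the documents give no SNR mean or SD. It does not measure harm in this trial. Nor do the documents support reading the point as a fault in the dose decisions themselves, or as a requirement that patients 4-6 pass the rule; the protocol sets no such requirement.

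**What to change.** 1. Use one wording of the primary objective in Sections 2 and 7.2, and state the SNR cut-off and EGFR score minimum in the Section 3.2 endpoint.
2. In Section 7.2, make the primary analysis the proportion of EGFR ≥ 1 locations with iFI SNR ≥ 10, by dose and by patient. Add the number of patients in whom every positive location reaches SNR ≥ 10, with its exact two-sided 95% interval.
3. At an expanded dose, show patients 4-6 separately from the first three.
4. Reconcile the definition of success in the synopsis, which requires all EGFR-positive samples, with Section 1.5, which omits that word.
5. Keep the t-tests, ANOVA and correlations, labelled as supporting analyses.

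The cost is wording in a few sections and one extra table. The iFI measurements and EGFR scores are already planned at each sampled location (Sections 6.1 and 6.3). The intervals will be wide, and at an expanded dose the unselected estimate rests on 3 patients.
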